10.5.1 Analyses of Co-primary Efficacy Endpoints

10.5.1.1 Primary Analyses of Co-primary Endpoints

To assess the co-primary endpoints of the mean percent change from baseline in LDL-C at weeks 10 and 12 and the percent change in LDL-C from baseline at week 12, a repeated measures linear effects model will be used on the FAS to compare the efficacy of evolocumab QM with placebo QM. The repeated measures model will include terms for treatment group, stratification factor, scheduled visit and the interaction of treatment with scheduled visit. Missing values will not be imputed for primary analysis.

To account for the repeated LDL-C measurements within a subject across the visits, the repeated measures linear effects model will use an unstructured covariance.

Multiplicity adjustment procedures are defined in [Section 10.1](#).

10.5.1.2 Sensitivity Analyses of Co-primary Endpoints

To evaluate the robustness of the analysis results, sensitivity analyses will be performed as follows:

- The primary analysis will be repeated using the CAS
- Non-parametric analyses will be performed
- Multiple imputation for subjects who discontinue IP with missing endpoint data
 - It will be assumed that the missing percent change values will be normally distributed with a mean 0 and a variance-covariance matrix the same as the observed variance-covariance matrix from subjects in the placebo group who did not discontinue IP with missing endpoint data.
 - If there are at least 25 subjects in each treatment group who discontinue IP but have non-missing endpoint data, an additional multiple imputation will be carried out utilizing the information from these subjects to impute the missing data for subjects who discontinue IP and have missing endpoint data

10.5.1.3 Covariate and Subgroup Analyses of Co-Primary Endpoints

In addition to the primary analysis specified in [Section 10.5.1.1](#), covariate-adjusted analyses of the co-primary efficacy endpoints will be performed as supportive analyses using the baseline covariates in [Section 4.2](#) in their original format, one at a time, in the primary model used in the primary analyses as appropriate.

Subgroup analyses on the co-primary efficacy endpoints will be conducted using the subgroups specified in [Section 7.3](#). Depending on the distribution of baseline LDL-C, analyses using different subgroups of baseline LDL-C will be performed if applicable. Treatment effect differences among subgroups, which represent subgroup by treatment

interactions, will be estimated and tested based on statistics from the subgroup repeated measures models.

For covariate and subgroup analyses, the stratification factor from the eCRF will be used. Differences in stratum assignment between data collection via IVRS and eCRF will be tabulated.

10.5.2 Analyses of Co-secondary Efficacy Endpoints

The statistical model and testing of the tier 1 co-secondary efficacy endpoints will be similar to the primary analysis of the co-primary endpoints. The co-secondary endpoints of achievement of target LDL-C < 70 mg/dL and LDL-C response of $\geq 50\%$ reduction from baseline will be analyzed using the Cochran-Mantel Haenszel (CMH) test adjusted by the stratification factor.

Analyses of the tier 2 co-secondary efficacy endpoints will use the same analysis model as the tier 1 endpoints, and testing will use a union-intersection test. For each tier 2 endpoint, the alternative hypothesis of the union-intersection test is that at least 1 of the treatment effects from the co-endpoints is not equal to zero.

Multiplicity adjustment procedures are defined in [Section 10.1](#).

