#### **10.5.3 Co-secondary Efficacy Endpoints**

Analysis of co-secondary endpoints will use the same analysis model as the co-primary endpoints. The co-secondary endpoints of LDL-C response (achievement of LDL-C < 70 mg/dL and achievement of > 50% LDL-C reduction from baseline) will be analyzed using the Cochran-Mantel Haenszel test adjusted by the stratification factor.

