3.2 Sample Size

The planned sample size for the comparison between evolocumab 420 mg QM and placebo at a ratio of 2:1 in the double-blind treatment period is 400 total subjects.

The primary analysis will require the 2-sided tests of co-primary endpoints to be significant at a level of 0.05. The planned sample size should provide adequate power to determine the superiority of evolocumab 420 mg QM relative to placebo as measured by the co-primary endpoints. From the phase 3 studies integrated efficacy analysis, the treatment effect of evolocumab 420 mg QM compared to placebo and the corresponding 95% confidence interval at week 12 was -60.39% [-64.57%, -56.21%], with treatment effect ranges between -55.1% to -62.33% from Studies 20110114, 20110115, and 20110117. The assumed treatment effect between evolocumab 420 mg QM and placebo for the co-primary endpoint at week 12 is 40%, with a common standard deviation (SD) of 20%. This SD assumption is based on evolocumab phase 3 results.

This sample size will provide approximately 99% power for the co-primary endpoint at week 12 in testing the superiority of evolocumab dose regimen over placebo, assuming a dropout rate of 10%.

From the phase 3 studies the treatment effects measured as mean of week 10 and week 12 were as large or larger than week 12 and highly correlated ($> 85\%$) with ones at week 12. Therefore the sample size as planned will provide at least 98% (99% \times 99%) power in testing the superiority of evolocumab over placebo on the co-primary endpoints.

From the phase 3 evolocumab studies the treatment effect of evolocumab over placebo in the percentage reduction in triglycerides at week 12 was approximately 12% with a

common SD of 35%. However, the SD for triglycerides in a diabetic population may be higher. [Table 1](#) displays the power associated with various SD assumptions.

Table 1. Power Associated With Standard Deviation Assumptions

Treatment effect = 12% reduction Sample size = 400 (5% dropout) Significance level = 5%	
Standard Deviation	Power
35	0.88
40	0.78
45	0.68
50	0.59

For HDL-C the treatment effect of evolocumab over placebo observed in the phase 3 studies at week 12 was a percentage increase of approximately 5% with a common SD of 15%. Assuming 400 subjects and a 5% drop out rate, this would provide approximately 86% power to test the superiority of evolocumab over placebo.

4. Study Endpoints and Covariates

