4.2 Planned Covariates

Stratification factor in the double-blind treatment period:

- LDL-C < 130 mg/dL vs ≥ 130 mg/dL

Baseline Characteristics:

- Age
- Sex (male, female)
- Race (black, white, and other)
- LDL-C
- Family history of premature coronary heart disease (CHD) (yes,no)
- PCSK9
- Region (North America, Europe, other)
- Body Mass Index (BMI)
- Hypertension (yes, no)

- Current smoker (yes, no)
- Additional baseline CHD risk factor (yes, no)
- Triglycerides
- Insulin Use (yes, no)
- Statin intensity (High/Moderate/Low intensity as per ACC/AHA guidelines)
- Lipid entry target (above both non-HDL-C and LDL-C entry criteria thresholds, above non-HDL-C entry criteria threshold only, and above LDL-C criteria threshold only)
- Presence of diabetes complications (0 complications, presence of 1 or more complications)

5. Hypotheses and/or Estimations

The primary statistical hypothesis of the co-primary endpoints is as follows:

The null hypothesis is that there is no mean difference in the mean percent change from baseline at weeks 10 and 12 or in the percent change from baseline at week 12 in LDL-C between evolocumab 420 mg QM and placebo, and the alternative hypothesis is that a mean difference does exist.

6. Definitions

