6.2 Demographics and Baseline Related Definitions

Age

Age will be calculated as the subject's age in years at enrollment as recorded on the eCRF.

Baseline Lipid and Lipid-related Parameters

Baseline values for fasting lipids (total cholesterol, HDL-C, LDL-C, VLDL-C and triglycerides), ApoA1, ApoB, Lp(a) and their derived parameters (eg, ratio between them) are defined as the mean of the two most recent non-missing fasting concentrations measured through central lab prior to or on Study Day 1. If for any reason only 1 value is available, then that value will be used as baseline.

Other Baseline Values

For PCSK9, the baseline value is defined as the average of the last two non-missing values collected prior to first IP administration. If for any reason only 1 value is available, then that value will be used as baseline.

For all other variables, the baseline value is defined as the last non-missing value collected prior to or on Study Day 1.

Change (absolute change) from Baseline

The arithmetic difference between a post-baseline value and baseline for a given time point:

Change (absolute change) from baseline = (post-baseline value – baseline value)

Percent Change from Baseline

The percent change from baseline for a given variable at a given time point is defined as:

$100 \times [(value \text{ at given time point} - \text{baseline value}) / \text{baseline value}]$

Baseline CHD Risk Factors

As all subjects in this study will have type II diabetes mellitus which is considered a CHD Risk Factor, a subject will be categorized as having an additional CHD Risk Factor (Y/N) if they have at least one from the list of the modified NCEP ATP III risk factors:

- current cigarette smoking
- hypertension
- family history of premature CHD as recorded on the eCRF
- low HDL-C defined as baseline HDL-C < 40 mg/dL in men and < 50 mg/dL in women.

Systematic Coronary Risk Estimation (SCORE) Categories

The SCORE system estimates the 10-year risk of a first fatal atherosclerotic event, whether heart attack, stroke, or other occlusive arterial disease, including sudden cardiac death ([ESC/EAS 2011](#)). The SCORE risk estimates will be computed from the high and low risk region tables based on sex and baseline smoking status, systolic blood pressure, total cholesterol and age.

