Endpoint	Primary Summary and Analysis Method (Specify Analysis Set if FAS is Not Used)	P-values from the Statistical Tests	Hierarchical Testing Procedure for testing of Treatment Effect vs. Placebo, as specified in the Multiplicity Adjustment Method diagram	Sensitivity Analysis
Co-Secondary Endpoints (Tier 2)				

Mean percent change from baseline at weeks 10 and 12Percent change from baseline at week 12 in each of the following lipid parameters: Lp(a), triglycerides, HDL-C and VLDL-C	Repeated measures model	For each lipid parameter, P2c=Union-intersection test p-value from the two contrasts of each co-endpoint pair	If P2a and all P2b's are significant through Hochberg method, → all P2c's from each lipid parameter will be tested through Hochberg method with $\alpha = 0.05$ Else (i.e. not all tier 1 co-endpoints are significant), → all P2c's from each lipid parameter will be tested through Hochberg method with $\alpha = 0.045$	n/a

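### The tier 2 lipid model omits the analysed lipid's own baseline: valid but inefficient, costing roughly 0.7 to 4 points of power for triglycerides and HDL-C under assumed correlations

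*SAP*

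**What the plan says.** The tier 2 co-secondary endpoints are percent change in Lp(a), triglycerides, HDL-C and VLDL-C. SAP 10.5.2 sets their analysis: "Analyses of the tier 2 co-secondary efficacy endpoints will use the same analysis model as the tier 1 endpoints". Tier 1 in turn follows the co-primary analysis, and SAP 10.5.1.1 lists the terms: "The repeated measures model will include terms for treatment group, stratification factor, scheduled visit and the interaction of treatment with scheduled visit". Protocol 10.5.3 says the same: "Analysis of co-secondary endpoints will use the same analysis model as the co-primary endpoints". SAP 4.2 defines the "Stratification factor in the double-blind treatment period" as LDL-C split at 130 mg/dL.

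Other baseline covariates, including continuous triglycerides, are listed in SAP 4.2. SAP 10.5.1.3 uses them only for LDL-C: "covariate-adjusted analyses of the co-primary efficacy endpoints will be performed as supportive analyses". In SAP Table 2 the tier 2 test is "P2c=Union-intersection test p-value from the two contrasts of each co-endpoint pair", and the sensitivity column is marked not applicable.

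The baselines themselves are defined. SAP 6.2 takes, for lipids and apolipoproteins, the "mean of the two most recent non-missing fasting concentrations measured through central lab" up to Study Day 1, or the single value if only one exists.

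**The concern.** An LDL-C stratum is not the baseline of a triglyceride, HDL-C, VLDL-C or Lp(a) measurement. Percent change carries its baseline in the denominator, so some negative correlation with baseline is expected from measurement variation alone. A model without that baseline leaves the associated variance in the residual.

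This hardly matters for LDL-C, where SAP 3.2 puts power at about 99%. It matters more in tier 2. On triglycerides the SAP itself warns: "However, the SD for triglycerides in a diabetic population may be higher". Its power table falls from 0.88 at SD 35 to 0.59 at SD 50, before any multiplicity step. What is at stake is some avoidable loss of precision, with no threat to validity.

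**Working it through.** **Inputs from SAP 3.2.** 400 subjects at 2:1, 5% dropout, 5% significance level (taken as two-sided). Triglycerides: effect 12%, SD 35, 40, 45 or 50. HDL-C: effect 5%, SD 15. Evaluable: 400 × 0.95 = 380, run as 254 evolocumab and 126 placebo.

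**Input not in the documents.** r, the within-arm correlation between a lipid's baseline and its percent change.

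**Step 1: reproduce the plan's powers.** SE = SD × √(1/254 + 1/126) = SD × 0.1090. For triglycerides at SD 35, SE = 3.81 and the noncentrality is 12 / 3.81 = 3.15. The noncentral t distribution gives power 0.881. All five stated powers are matched (column r = 0 below). A separate normal approximation with 380 evaluable gives 0.883, 0.787, 0.688, 0.597 and 0.865.

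**Step 2: add the lipid's own baseline.** The residual SD becomes SD × √(1 − r²), with one degree of freedom lost. At r = 0.3, √(1 − 0.09) = 0.954. For triglycerides at SD 35, SE = 3.64, noncentrality is 3.30 and power is 0.908.

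| Endpoint | SAP | r = 0 | 0.1 | 0.15 | 0.3 | 0.5 |
|---|---|---|---|---|---|---|
| Triglycerides, SD 35 | 0.88 | 0.881 | 0.884 | 0.888 | 0.908 | 0.952 |
| Triglycerides, SD 40 | 0.78 | 0.784 | 0.788 | 0.793 | 0.821 | 0.887 |
| Triglycerides, SD 45 | 0.68 | 0.685 | 0.689 | 0.695 | 0.725 | 0.805 |
| Triglycerides, SD 50 | 0.59 | 0.594 | 0.598 | 0.603 | 0.634 | 0.718 |
| HDL-C, SD 15 | 0.86 | 0.862 | 0.866 | 0.870 | 0.892 | 0.941 |

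The gain is 0.3 to 0.4 points at |r| = 0.1, 0.7 to 4.1 points over 0.15 to 0.3, and 7 to 12 points at 0.5. Confidence intervals narrow by 1 − √(1 − r²): 0.5%, 1.1%, 4.6% and 13.4% at |r| = 0.1, 0.15, 0.3 and 0.5.

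**Step 3: is 0.15 to 0.3 plausible?** Log-normal lipids were simulated with within-subject variation only, baseline as the mean of two values, and the percent-change SD set to 35, 45 or 15. The free input is the reliability of one measurement, which the documents do not give. At reliability 0.6 to 0.8, |r| is 0.16 to 0.29. At 0.9 it is about 0.09 to 0.13, and the gain is then under 1 point.

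**Step 4: unequal slopes.** With one common baseline slope, 2:1 allocation and equal SDs, the proportional variance reduction is (pooled standardised slope) × (placebo standardised slope). Taking 0.3 in evolocumab:

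- Placebo 0.3: 0.30 × 0.30 = 9.0%, the case in the table.
- Placebo 0.15: pooled slope (2 × 0.3 + 0.15) / 3 = 0.25, and 0.25 × 0.15 = about 3.7%. The gain is 1.2 to 1.6 points.
- Placebo 0: no reduction and no gain.

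**Step 5: closer to the planned test.** The SAP gives no formula for the union-intersection p-value, so a Bonferroni minimum-p and a 2-df Wald test were both tried. The assumptions were equal effects at weeks 10 and 12, visit correlation 0.6 to 0.8, equal slopes and alpha 0.05. For triglycerides at SD 35, 40 and 50 and for HDL-C, the gain is 0.8 to 1.3 points at |r| = 0.15 and 3.0 to 5.5 points at 0.3. Separately, a single test at the strictest Hochberg level for four endpoints, 0.05 / 4 = 0.0125, gains 1.0 to 5.0 points over the same range of |r|. The full Hochberg procedure was not modelled.

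**The case against.** The strongest reply is that nothing here is wrong. The protocol and SAP agree, one model serves all continuous lipid endpoints, the comparison is valid, and no tier 2 power target is set that could be missed. That stands, and it is why the point is optional.

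The second reply is that the size rests on quantities the documents do not give. This also stands. There is no stated correlation, averaging two baseline values weakens it, and the gain depends on the placebo-arm slope and can be zero. SAP 3.2 also does not say whether the phase 3 SDs were already baseline-adjusted; if they were, part of the gain is already counted. Equal slopes are nevertheless a reasonable central case for effects as small as 12% and 5%, because regression to the mean acts in both arms. A treatment effect that varies with baseline could change that.

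The third is that the 0.7 to 4.1 point range is for a single test, not the planned one. True, but the approximations closer to the planned test give gains of similar size, slightly larger at the top.

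Finally, SAP 9.6 allows alternative methods if distributional assumptions fail. That provision concerns distributional fit and does not supply baseline adjustment.

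**Conclusion.** The concern holds as a matter of efficiency. No planned analysis adjusts a tier 2 lipid for its own baseline. On the SAP's own power basis the cost is 0.7 to 4.1 points for triglycerides and HDL-C, assuming |r| of 0.15 to 0.3, equal slopes in the two arms and SDs not already adjusted. It may be negligible or nil if those assumptions fail. Nothing can be computed for VLDL-C or Lp(a), because the documents give neither an effect nor an SD for them. Type I error and bias are unaffected. This is a worthwhile optional improvement; confidence in its size is medium.

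**What to change.** Before unblinding, amend SAP 10.5.2 so that the tier 2 repeated measures model adds the continuous baseline of the analysed lipid and its interaction with visit. Keep the stratification factor. Report the model without baseline as the tier 2 sensitivity analysis in Table 2. The same term could be extended to the other continuous co-secondary endpoints for consistency; the co-primary model needs no change.

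The cost is one or two degrees of freedom per model, some SAP text and code, and no new data. Because Protocol 10.5.3 fixes the current model and SAP section 11 declares no departures, the change must be recorded there. Made after unblinding, it could look data-driven.

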10.5.3 Analyses of Exploratory Endpoints

Exploratory endpoints related to lipid parameters and PCSK9 will be summarized by randomized treatment group and by scheduled visit using descriptive statistics.

HbA1c and FBG will be summarized at each scheduled assessment by actual treatment group.

Area under the curve (AUC) and incremental AUC will be calculated for laboratory parameters collected for the MMTT at day 1 and at week 12. Change and percent change from day 1 to week 12 in AUC and incremental AUC will be provided by actual treatment group. Analysis will be performed separately for those subjects who have the extended timepoint assessments.

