#### 7.4.3 Mixed Meal Tolerance Test Extended Timepoints

Approximately the first 100 subjects not on prandial insulin or GLP-1 agonists will undergo the MMTT Extended Timepoints assessments. The assessments consist of 4 postprandial blood draws in the MMTT on day 1 and week 12. Postprandial blood draws for subjects participating in the assessments will be at the following timepoints after consumption of the standardized meal:

- $30 \pm 10$  min
- $60 \pm 10$  min
- $120 \pm 10$  min
- $180 \pm 10$  min

The same postprandial analytes will be measured at each of these timepoints.

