2.4 Exploratory

To describe the effects over time of SC evolocumab QM compared with placebo QM, in subjects with type 2 diabetes mellitus and hypercholesterolemia or mixed dyslipidemia in combination with maximally tolerated dose of statin of at least moderate-intensity PO QD on:

- Change from baseline in proprotein convertase subtilisin/kexin type 9 (PCSK9) levels and on change from baseline and percent change from baseline of LDL-C,

total cholesterol, non-HDL-C, ApoB, VLDL-C, HDL-C, apolipoprotein A-I (ApoA1), triglycerides, and Lp(a)

- Change and percent change from baseline on fasting and postprandial plasma laboratory parameters of interest including glucose, insulin, pro-insulin, C-peptide, fatty free acids, glucagon, lipids, chylomicrons, ApoB48, interleukin-6 (IL-6), adiponectin after a mixed meal tolerance test (MMTT).
- The relationship between novel and established biochemical cardiovascular and lipid biomarkers and effects of evolocumab
- Potential correlations of study data including the subject response to evolocumab with genetic variation in markers of PCSK9 signaling, low-density lipoprotein receptor (LDLR) turnover, cholesterol metabolism, inflammation, and plaque stability in subjects consenting to the optional pharmacogenetic analysis

3. Study Overview

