3.1 Study Design

This is a phase 3b, multicenter, double-blind, randomized, placebo-controlled study designed to assess the efficacy and safety of evolocumab in subjects with type 2 diabetes mellitus with hypercholesterolemia or mixed dyslipidemia. All subjects will be treated with maximally tolerated dose of statin of at least moderate-intensity (intensity as specified by the 2013 ACC/AHA guideline on the treatment of blood cholesterol to reduce atherosclerotic cardiovascular risk in adults; see Protocol Appendix D). Baseline lipid-lowering therapy is expected to be continued unchanged throughout the study.

The study will consist of 2 periods:

- Screening up to 6 weeks including a 4-week lipid stabilization and placebo injection
- Double-blind treatment period (12 weeks)

After signing the informed consent, subjects will enter the screening/lipid stabilization period during which their appropriate-dose statin is continued. Screening laboratory tests including lipid testing will be conducted during week 2 of the screening/lipid stabilization period. Subjects must tolerate a SC injection of placebo with device anticipated to be used during the study (either AI/Pen or AMD) prior to randomization. Subjects who meet all eligibility criteria at the end of the screening/lipid stabilization period will be randomized in a 2:1 ratio into the following treatment arms:

- SC evolocumab 420 mg QM (~270 subjects)
- SC placebo QM (~130 subjects)

Randomization will be stratified by LDL-C (< 130 mg/dL vs \geq 130 mg/dL).

Day 1 is defined as the calendar day when treatment with investigational product (IP) is initiated. Subjects should initiate their first dose of IP within 5 days of randomization.

During the double-blind treatment period, study visits will occur at day 1, week 8, week 10, and week 12, with baseline evaluations performed on day 1 of treatment before subjects receive the first dose of IP. All subjects will complete a MMTT at the day 1 and week 12 study visits with a baseline (0 hours) and 2-hour (± 10 min) postprandial blood collection after the meal. Up to approximately 100 subjects not treated with prandial insulin or glucagon-like peptide-1 (GLP-1) agonists will participate in MMTT Extended Timepoints assessments with 3 additional postprandial blood draws at 30 minutes (± 10 min), 1 hour (± 10 min), and 3 hours (± 10 min) after the meal in addition to the blood draws at 0 and 2 hours (± 10 min) after the meal for all subjects.

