10.1 General Principles

To evaluate efficacy and safety of 12 weeks of evolocumab 420 mg QM compared with placebo, the primary analysis will be performed when all randomized subjects in the double-blind treatment period have either completed all the scheduled study visits in the double-blind treatment period or have early terminated from the study. At that time, the database of the study will be cleaned, processed and a snapshot will be taken; the study will also be unblinded.

Based on the snapshot, efficacy and safety analyses will be performed on the FAS. Unless specified otherwise, the FAS will be the default analysis set in this study and data will be summarized by randomized treatment group.

Subject disposition, demographics, baseline characteristics and exposure to IP will be summarized by treatment group. Summary statistics for continuous variables will include the number of subjects, mean, median, standard deviation, or standard error,

[figure not shown]
minimum, and maximum. For categorical variables, the frequency and percentage will be given.

Methods of handling missing data for efficacy endpoints will be described below. Missing data will not be imputed for safety endpoints.

Multiplicity Adjustment Method

Methods of adjusting for multiplicity due to multiple endpoints (primary and secondary efficacy endpoints) in order to preserve the familywise error rate at 0.05 are described in Figure 1.

Figure 1. Multiplicity Adjustment Methods

Testing of each co-endpoint pair will result in a single p-value, and for co-secondary endpoints these p-values will then be used in the Hochberg procedure. The following method will be used to preserve the family wise error rate for the co-primary and co-secondary endpoints:

- If the treatment effect from the primary analysis of the co-primary endpoints are both significant at a significance level of 0.05, statistical testing of the tier 1 co-secondary efficacy endpoints will follow the Hochberg procedure at a significance level of 0.005 ([Hochberg, 1988](#))

- If all tier 1 co-secondary efficacy endpoints are significant, the tier 2 co-secondary efficacy endpoints will be tested using the Hochberg procedure at a significance level of 0.05.
- If not all tier 1 co-secondary efficacy endpoints are significant, the tier 2 co-secondary efficacy endpoints will be tested using the Hochberg procedure at a significance level of 0.045 ([Wiens, 2003](#)).

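### SAP 10.5.3 plans percent change in incremental AUC without defining incremental AUC or saying what happens when its Day 1 value is zero, near zero or negative

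*SAP*

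**What the plan says.** SAP 10.5.3 first states that "Area under the curve (AUC) and incremental AUC will be calculated for laboratory parameters collected for the MMTT at day 1 and at week 12". It then commits to four summaries: "Change and percent change from day 1 to week 12 in AUC and incremental AUC will be provided by actual treatment group". Those subjects who have the extended sampling are to be analysed separately.

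Incremental AUC is named there but not defined. Neither document says whether it is the net area above the fasting value or the positive part only.

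The general formula is in SAP 6.2: "The percent change from baseline for a given variable at a given time point is defined as" 100 times the difference from baseline, divided by baseline. It sets no condition on the denominator.

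On sampling, SAP 3.1 states: "All subjects will complete a MMTT at the day 1 and week 12 study visits with a baseline (0 hours) and 2-hour" postprandial sample. Only a subset has more: "Approximately the first 100 subjects not on prandial insulin or GLP-1 agonists will undergo the MMTT Extended Timepoints assessments" (Protocol 7.4.3), with draws at 30, 60, 120 and 180 minutes.

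The MMTT objective in SAP 2.4 is descriptive: "To describe the effects over time of SC evolocumab QM compared with placebo QM". It covers eleven analytes or analyte groups (SAP 4.1.4).

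**The concern.** Percent change is a sensible summary when the denominator is positive and well away from zero. Total AUC of a concentration meets that condition. Incremental AUC need not: it is a difference, and with two samples it is a single difference between two measurements. Neither document says that every listed analyte must rise after the meal.

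For an analyte whose Day 1 response falls, or is small relative to its spread between subjects, this one summary can show undefined values, reversed signs or an unstable mean. It could then contradict the absolute change in the same output. If the definition and any exclusion rule are left until unblinded data are in hand, they would be chosen with the results visible.

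**Working it through.** **Plan's own figure.** There is none to reproduce. No power, alpha or sample-size figure bears on this output.

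**Inputs from the documents.** 400 subjects randomized 2:1 (SAP 3.2). Samples at 0 and 120 minutes for all, extended sampling for about 100 (SAP 3.1, Protocol 7.4.3). Percent change = 100 x (value - baseline) / baseline (SAP 6.2).

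**Assumptions.** The trapezoidal rule; a 2:1 split among the 400 - 100 = 300 two-point-only subjects (about 200 and 100); and, for the size, normally distributed incremental AUC with a stated mean/SD. The documents give no mean, SD or correlation.

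**Step 1: the two-point form.**
- AUC = 60 x (C0 + C120)
- Net incremental AUC = AUC - 120 x C0 = 60 x (C120 - C0)

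The net value is zero or negative whenever the 2-hour value is at or below fasting.

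**Step 2: the formula applied to a negative denominator.** With Day 1 = -600 and week 12 = -300, the change is +300, but the percent change is 100 x 300 / (-600) = -50%. A rise is reported as a fall. With a positive-only definition the Day 1 value is 0 and the ratio is undefined.

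**Step 3: the same absolute change, different denominators.** Assumed fasting level 100 at both visits and time in hours, so that net incremental AUC = C(2h) - C(0). Every row is a true change of +10.

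| Day 1 incremental AUC | Percent change, incremental AUC | Percent change, total AUC |
|---|---|---|
| 40 | +25% | +4.2% |
| 1 | +1000% | +5.0% |
| 0 | undefined | +5.0% |
| -1 | -1000% | +5.0% |
| -10 | -100% | +5.3% |

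Total AUC behaves well throughout, so the fault is specific to incremental AUC.

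**Step 4: how often, and how unstable (net definition).** The share of negative Day 1 values is Phi(-mean/SD). The other columns come from 4,000 simulated trials with no true change and a Day 1 to week 12 correlation of 0.5. They use a full evolocumab arm of 270, whereas the counts use the two-point-only subjects.

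| Mean/SD | Share negative | Expected count, of 200 and 100 | 95% range of arm mean percent change, n = 270 | Centre of arm median |
|---|---|---|---|---|
| 0.5 | 31% | 62 and 31 | not tabulated | -39% |
| 1 | 16% | 32 and 16 | -755% to +890% | -20% |
| 2 | 2.3% | 5 and 2 | -266% to +233% | -2% |
| 3 | 0.13% | 0.3 and 0.1 | -21% to +37% | 0% |
| 4 | 0.003% | none | 0% to +8% | 0% |

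At mean/SD 1 the median shift is -28% with correlation 0.3 and -8% with correlation 0.8. With a normal denominator the ratio has no finite expectation, so the limits of the mean move between simulation runs. The ranges at mean/SD 1 and 2 show instability and are not an effect size.

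**Step 5: positive-only definition.** With zero denominators set to missing, the median shift is about -25% at mean/SD 0.5 and -11% at 1. It is smaller than under the net definition but still present, and the subjects with a zero Day 1 value drop out.

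**Step 6: does another provision cover this?**
- SAP 9.3 deals with missing lipid values and incomplete dates.
- SAP 9.5 allows optional sensitivity analyses for extreme outliers. These cannot define a ratio over zero or correct a sign.
- SAP 9.6 is limited to the primary and secondary co-endpoints.
- SAP 10.1 plans a median ("Summary statistics for continuous variables will include the number of subjects, mean, median, standard deviation, or standard error"), which helps only in part, as Step 4 shows.

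**The case against.** The size has no empirical basis in the documents. Mean/SD, normality and correlation are all assumed, no analyte can be assigned to a row, and the results run from serious to negligible. That stands, and it is why a range is given.

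The within-arm median shift is not a bias in the treatment comparison. With no true change it is the same in both arms, so the difference between arm medians stays centred on 0 (95% range -21 to +20 points at mean/SD 1, -6 to +7 at 4). That also stands. It does not rescue the arm-level values, the means or the reversed signs.

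There are partial safeguards. Absolute change and medians are planned, and a reversed sign would be visible beside the absolute change. This limits the harm but leaves a planned output that may be misleading.

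The strongest objection is to the remedy. The gap is a missing rule, and deleting the summary goes further than filling the gap. Protocol 10.1.1.3 and SAP 4.1.4 list percent change for the MMTT parameters, incremental AUC is arguably the measure that isolates the meal response, and SAP section 11 declares no changes from the protocol. One could instead define incremental AUC, pre-specify when percent change is set to missing, and report the counts. That is a workable alternative, but it excludes subjects according to their Day 1 response and still leaves extreme ratios from small positive values unless a cut-off is also chosen. Protocol 10.1.1.3 does not mention AUC, and percent change in AUC would remain, so removing this one summary does not breach the listed endpoint.

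**Conclusion.** The concern holds and is minor. Followed as written, the plan gives reversed signs or undefined values whenever the Day 1 2-hour value is below fasting, and extreme ratios when the Day 1 increment is small. That much is arithmetic and needs no distributional assumption.

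How often it would occur is unknown. Under normality it ranges from about a third of subjects at a mean/SD of 0.5 to practically none at 4.

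Change in AUC, percent change in AUC and absolute change in incremental AUC are unaffected. The output is exploratory, has no planned test and lies outside the multiplicity procedure.

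**What to change.** In SAP 10.5.3, replace the second sentence of the MMTT paragraph with wording such as:

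> Incremental AUC is the net area relative to the pre-meal (0 minute) value, by the trapezoidal rule. Change from day 1 to week 12 will be provided for AUC and incremental AUC, and percent change will be provided for AUC only, by actual treatment group.

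If a positive-only area is preferred, state that definition instead. Percent change in incremental AUC should be dropped in either case. If the sponsor wishes to keep it, the minimum is a definition, a rule for when it is set to missing, and a count of the subjects affected in each arm. The wording should be settled before unblinding.

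The cost is two sentences of SAP text and one fewer output per analyte, with no new data or programming. What is lost is a scale-free summary of incremental AUC.
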